6.1.2 Exclusion Criteria

The subject is participating in another device trial or any other clinical trial where the study procedure or treatment might confound this study's endpoint.

6.2 Withdrawal and Replacement of Subjects

While study withdrawal is discouraged, subjects may withdraw from the study at any time, with or without reason and without prejudice to further treatment. Withdrawn subjects will not undergo any additional follow-up, nor will they be replaced. If a subject chooses to withdraw from the Registry, the reason(s) for withdrawal will be recorded on the appropriate electronic Case Report Form (eCRF) and in the medical record.

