4.1 Primary Clinical Outcome

1. Severity of disability at Day 90 (± 14) assessed by mRS with a good functional outcome defined as mRS of 0-2 for each technique

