4.5 Safety Outcomes

1. All-cause mortality and stroke-related mortality up to Day 90 (± 14)
2. Device and/or procedure related SAEs up to Day 90 (± 14)
3. Neurological deterioration at 24 (-6/+24) hours post procedure defined as a four or more point increase in NIHSS from baseline
4. Symptomatic intracranial hemorrhage (SICH) adapted from European Cooperative Acute Stroke Study (ECASSIII) as any apparent extravascular blood in the brain or within the cranium that is associated with clinical deterioration defined by a NIHSS increase of four points or more from baseline up to 24 (-6/+24) hours
5. Embolization to New Territory adjudicated by core lab

Document Title: ASSIST™ Registry Protocol

Document Number: CDM10001414

Rev: AB

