7.7 Day 90 (\pm 14 days)

At Day 90 (\pm 14 days) the following study assessments should be performed:

- mRS (A telephone assessment may be conducted, but in-person is strongly encouraged)
- EuroQol (EQ5D5L)
- Device and/or Procedure Related AEs
- All SAEs
- All Deaths

Any death or device and/or procedure related AEs and all SAEs should be reported to Stryker Neurovascular within 24 hours of becoming aware. For all subjects who expire prior to the Day 90 assessment, available information regarding the primary cause of death and date/time of death will be recorded.

Stryker Neurovascular

Document Title: ASSIST™ Registry Protocol

Document Number: CDM10001414

Rev: AB

Table 4. Time and Events Schedule

Time and Events Schedule						
Assessments:	Pre-procedure (Screening /Baseline)	Procedure	24 (-6/+24) hrs. post procedure	Discharge (or Day 5-7 whichever comes first)	Day 30 ±14 days	Day 90 ±14 days
Inclusion/Exclusion Criteria	✓					
Informed Consent*	✓					
Demographics & Medical History	✓					
Baseline Labs	✓					
mRS**	✓			✓	✓	✓
NIHSS Assessment	✓		✓	✓		
EuroQol (EQ5D5L)						✓
Stroke Onset	✓					
CT/MR ^Y	✓		✓			
Angiogram Procedure Information **** ^Y		✓				
Hospital Stay/Discharge Disposition****				✓		
Adverse Events [‡]		✓	✓	✓	✓	✓
Study Completion						✓

*Written Informed Consent must be obtained prior to subject enrollment and any data entry.

**Telephone mRS assessment is acceptable if subject is not able to return in person.

***See study binder for worksheets listing items to record during the procedure.

****Study Staff should review the study requirements with the subject and arrange all follow-up visits at discharge.

[‡] All AEs during procedure, only Device Related and/or Procedure Related AE & all SAE, death post procedure.

^Y CT/MR and Angiographic images will be de-identified with subject ID# if submitted to SNV or the core lab.

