12 ADVERSE EVENTS

An Adverse Event (AE) is any untoward medical occurrence, unintended disease or injury, or untoward clinical sign (including abnormal laboratory findings) in subjects, users or persons, whether or not related to the medical device(s). All subjects will be assessed for complications or adverse events during the procedure and at all follow-up visits per section 7.4-7.7, and recorded on the AE case report form. Data to be collected will include the AE event term, onset and resolution dates (or whether the AE is ongoing), seriousness, management/treatment, outcome, and determination of the relationship to the devices and the index procedure. All AEs will be followed until resolution or an appropriate endpoint is reached, or until the subject has completed or discontinued the registry.

More specifically, the following adverse events are to be reported on the Adverse Event case report form:

- All AEs and serious adverse events (SAE) that occur during the procedure
- Only device and/or procedure related AEs post procedure through Day 90
- All SAEs post procedure through Day 90

STRYKER CONFIDENTIAL - THIS DOCUMENT CONTAINS CONFIDENTIAL AND PROPRIETARY INFORMATION THAT IS THE PROPERTY OF STRYKER CORPORATION. NEITHER THIS DOCUMENT NOR THE INFORMATION HEREIN MAY BE REPRODUCED, USED, OR DISCLOSED TO ANY THIRD PARTY WITHOUT THE PRIOR WRITTEN CONSENT OF STRYKER CORPORATION.

Stryker Neurovascular

Document Title: ASSIST™ Registry Protocol

Document Number: CDM10001414

Rev: AB

NOTE: Any “prolonged” hospitalization(s) related to the study procedure which is considered standard of care due to subject age, co-morbidities or neurological status at presentation will not be considered SAEs

- Any event causing neurological deterioration defined as a ≥ 4 point increase on the NIHSS from baseline (e.g. cerebral edema, brain herniation, stroke progression) which is related to the index stroke
- Any event causing symptomatic intracranial hemorrhage (SICH) defined as a ≥ 4 point increase in NIHSS from baseline for which the hemorrhage is determined to be the cause
- All device-related adverse events (also known as “adverse device effects” [ADEs])
- All serious adverse device effects (SADEs)
- All unanticipated serious adverse device effects (USADEs)
- All adverse events that result in death through Day 90

NOTE: Death should not be recorded as the AE term but should be reflected as an outcome to a specific AE

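### Section 6.2 has one category of withdrawal that ends all registry follow-up, so Day 90 status goes uncollected even for withdrawn subjects who would allow a telephone call or chart check

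*Combined protocol and SAP*

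**What the plan says.** Section 6.2 lets subjects leave freely: "subjects may withdraw from the study at any time, with or without reason and without prejudice to further treatment". It then gives a single consequence: "Withdrawn subjects will not undergo any additional follow-up, nor will they be replaced". The only item it asks for at that point is the reason: "the reason(s) for withdrawal will be recorded on the appropriate electronic Case Report Form (eCRF) and in the medical record". It names no final mRS, vital status check or SAE outcome.

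Section 12 matches this. Adverse events are followed to resolution, to another suitable endpoint, "or until the subject has completed or discontinued the registry".

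The outcomes affected run to Day 90. The primary clinical outcome (section 4.1) is disability at Day 90, "assessed by mRS with a good functional outcome defined as mRS of 0-2 for each technique". The safety outcomes (section 4.5) include "All-cause mortality and stroke-related mortality up to Day 90" and "Device and/or procedure related SAEs up to Day 90".

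Section 7.7 accepts a remote primary outcome: "mRS (A telephone assessment may be conducted, but in-person is strongly encouraged"). Section 7.6 has the same allowance at Day 30. The footnote to Table 4 is narrower and accepts a telephone mRS for subjects who cannot come back in person. No remote mode is stated for adverse event or vital status checks.

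**The concern.** Section 6.2 does not separate a subject who wants no more visits from one who withdraws permission for all data collection. Once a site ticks withdrawn, both are handled alike, although the first might accept one telephone call or a look at the chart.

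At stake are the primary clinical outcome and 90-day mortality, both of which need status at or up to Day 90. Missing values of this kind are partly avoidable. They could also be related to outcome: well-recovered subjects may see no reason to continue, and families of severely disabled subjects may want no further burden. The documents neither show nor exclude such a pattern.

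**Working it through.** **Which subjects are affected**

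1. Recorded as withdrawn before Day 90: section 6.2 stops follow-up and section 12 stops adverse event follow-up. Day 90 mRS, later death and the registry outcome of an open related SAE are not sought.
2. Stops visits but stays enrolled: sections 7.6 and 7.7 allow the mRS by telephone, so the primary outcome can still be obtained.
3. The text does not say which of these applies to a subject who declines visits. Inclusion criterion 4 requires willingness to comply with follow-up, section 7.5.1 has staff instruct subjects to return, and the Table 4 footnote speaks of inability rather than unwillingness. A site could reasonably choose either.

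**The plan's own figures (section 8.1)**

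- Inputs: assumed rate 50%, 95% Wald interval 47% to 53%, 1200 evaluable, 20% loss to follow-up.
- Inflation: 1200 / (1 - 0.20) = 1500, as stated.
- Half-width at 1200: 1.96 × √(0.25/1200) = 2.83 points, inside the 3-point target. The exact binomial probability that the estimate falls in 47% to 53% is 0.965, consistent with the stated probability above 0.9.

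The sample size is not in dispute.

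**Size of the uncertainty from withdrawal**

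The withdrawal rate is an assumption, taken as 1% to 5%. With observed rate r and missing fraction m, the overall rate lies between r(1 - m), if none of the missing had the event, and r(1 - m) + m, if all did. The width is m, for mRS 0-2 and mortality alike, and comes on top of any other loss.

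| Assumed withdrawal | Subjects of 1500 | Bounds at r = 50% | Width |
|---|---|---|---|
| 1% | 15 | 49.5% to 50.5% | 1 point |
| 5% | 75 | 47.5% to 52.5% | 5 points |

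For comparison, the planned interval is 53 - 47 = 6 points wide. Obtaining status for half of those who withdraw would halve the widths, to 0.5 and 2.5 points.

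A less extreme case: if withdrawn subjects had a 30% or 70% rate instead of 50%, the true overall rate at 5% withdrawal would be 0.95 × 50 + 0.05 × 30 = 49.0%, or 0.95 × 50 + 0.05 × 70 = 51.0%. The estimate from observed subjects would be off by 1 point. At 1% withdrawal it would be off by 0.01 × 20 = 0.2 points.

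**Precision against bias**

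- The half-width is 2.53 points with all 1500 observed and 2.60 with 1425 (5% missing), so little precision is lost.
- In the smallest planned group, 72 subjects, four withdrawals (illustrative) give 4/72 = 5.6 points. The sampling half-width there is already 1.96 × √(0.25/72) = 11.5 points. Even in that group the issue is possible bias, not precision.

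**The case against.** The strongest reply is that this is an observational registry of a single procedure. There is no continuing study treatment to stop, so withdrawal means withdrawal from data collection, and ending follow-up respects consent. That is a fair default for someone who withdraws all consent. It does not cover someone who would permit limited contact.

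A reader might infer that the plan forfeits Day 90 data for everyone who merely wants to stop visits. The documents do not support that. Section 6.2 concerns leaving the study, and the telephone mRS lets such a subject remain enrolled.

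A reader might also infer that an ongoing device-related SAE is dropped altogether. That is not supported either. Section 12.2 sends device-related events to the sponsor's complaint process, with further contact to sites, and section 12.5 provides vigilance reporting; neither is made conditional on participation. That process is separate from registry endpoint collection, however, and the complaint route covers device-related events, not events related only to the procedure.

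It can be argued too that section 6.2 ends visits and not chart review, since sections 7.6 and 7.7 ask for cause and date of death for all subjects who die before the assessment, with no exception for the withdrawn. The text is open on this. Nothing tells sites to look for deaths after withdrawal, and section 12 points the other way.

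The 20% allowance in section 8.1 exceeds the withdrawal rates assumed here. It protects precision but does not protect against bias if those lost differ from those kept.

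Two limits stand. The direction and existence of bias are conjecture. The consent template (Appendix D) was not available for this review and may already address data use after withdrawal; nothing is inferred from that.

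**Conclusion.** The point holds in a limited form. For subjects recorded as withdrawn before Day 90, sections 6.2 and 12 leave the Day 90 mRS, later death and the registry outcome of open related SAEs uncollected, even where the subject would allow a call or chart check. Data gathered before withdrawal are not affected, since nothing says they are discarded. The boundary between declining visits and withdrawing is left to each site.

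On an assumed 1% to 5% withdrawal, the best-to-worst-case range is 1 to 5 points wide, and the bias under a 20-point difference in outcome is 0.2 to 1 point. No material change to a result has been shown. This is avoidable missing data on the main outcomes that can be reduced at little cost; it is not a flaw that invalidates the design.

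**What to change.** Amend section 6.2 so that the withdrawal eCRF records one of two categories:

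- (a) The subject stops visits but permits limited follow-up. Collect the Day 90 mRS by telephone or from the medical record, vital status with date and cause of death, and the outcome of open device- or procedure-related SAEs to Day 90 from the record.
- (b) The subject withdraws all consent. Collect nothing further except where local law permits.

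State that declining visits alone is not withdrawal, and bring the Table 4 footnote into line with sections 7.6 and 7.7. Align the adverse event follow-up sentence in section 12. Check the consent template for consistency and amend it if needed. Report the number in each category by technique.

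The cost is protocol wording, possibly consent wording, one eCRF field, and a few calls or chart checks by existing site staff. The gain is only partial where passive follow-up is not permitted. The sample size does not change.

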6.3 Enrollment Controls

Enrollment will be monitored to ensure that no more than the specified number of subjects is enrolled. The EDC System will be used and monitored to ensure maximum enrollment is contained.

7 STUDY PROCEDURES

7.1 Written Informed Consent

An Informed Consent Form (ICF) template is provided in **Appendix D** for the Investigator to prepare for Institutional Review Board (IRB)/Ethics Committee (EC) submission. The ICF must be prepared in the language(s) of the potential subject population, document version identified, and approved by the site IRB/EC. A copy must be provided to Stryker Neurovascular. Modifications to the form must be approved by Stryker Neurovascular prior to implementation.

An ICF must be obtained pre-procedure or up to 48 hours post- procedure. The ICF must be obtained prior to data entry into the ASSIST Registry EDC. The subject or the subject's legally authorized representative (LAR) will be asked to sign the ICF. Study personnel should document the consent process in the subject's medical record per Good Clinical Practice (GCP). The subject or LAR is to be provided a copy of the signed ICF.

7.2 Pre-Procedure Assessments

The following pre-procedure data will be obtained for subjects enrolled in the Registry:

- Inclusion/Exclusion Criteria
- Informed Consent
- Demographics & Medical History
- Baseline Labs
- Baseline Pre-stroke mRS
- Post-stroke NIHSS assessment
- Stroke Onset
- Neuroimaging (CT, MR)

Document Title: ASSIST™ Registry Protocol

Document Number: CDM10001414

Rev: AB

7.3 Procedure/Treatment

7.3.1 Angiogram Procedure

For subjects enrolled in this Registry, treatment initiation will be defined as the date and time of groin puncture.

A diagnostic angiogram must be performed to determine the appropriate procedural technique to be used for reperfusion. The following will be collected for subjects enrolled in the Registry:

- The occlusion location(s)
- A single image when all devices are in position for each pass. This will be the start time of the pass.
Please note: A single image must be performed, even if there is failure to access the clot.
- Angiographic evaluations with clear visualization of the target artery before treatment initiation, after each attempt to remove thrombus from the occlusion location, and post-procedure to determine vessel patency. It is considered best practice to utilize the same angiographic orientation before and after device use as well as post-procedure and to include late venous phase in the angiogram acquisition to allow a valid analysis of the reperfusion status of the vessel(s).
- Expanded TICI scores for each pass within the vascular territory being treated. Time of eTICI assessment will be the stop time of each pass.

Sites will submit all de-identified angiographic data for subjects enrolled in the Registry, rather than pre-selecting a subset of images. If angiographic images are missing from the sequence of acquisitions, the core lab will request the site to resend the de-identified angiography dataset.

In the event of a procedural complication or adverse event, detailed angiographic images shall be obtained and submitted. All adverse events and/or device malfunctions that occur during the procedure must be documented and recorded on the applicable CRFs.

7.3.2 Thrombectomy Procedure

The thrombectomy techniques that will be evaluated in the ASSIST Registry are included in Table 2. Additionally, Table 3 includes examples of SNV devices that can be used for each technique. Note that not all devices in Table 3 have market approval in all global regions for the intended use as described in Table 2. Physicians should use each device according to the intended use statement in the most current version of the IFU with regards to the devices' intended use, compatibility, preparation and the recommended retrieval procedure.

Stryker Neurovascular

Document Title: ASSIST™ Registry Protocol

Document Number: CDM10001414

Rev: AB

Table 2. Procedural Techniques Evaluated in the ASSIST Registry

Technique	Description
SR Classic	
Definition: Referred to as the “SR Classic” technique which combines a BGC for proximal flow control and retrieval with the Trevo Retriever.
 
Procedural technique: The BGC is placed at the desired location. Using a guide wire, a microcatheter is then navigated through the BGC to the site of occlusion. Position the microcatheter tip distal to the thrombus and remove the guidewire. The retriever is delivered through the microcatheter and is deployed per IFU and is allowed to expand and integrate into the clot. Prior to retriever retraction, the BGC is inflated (to control antegrade flow in the ICA). During retrieval, it is recommended that aspiration is applied through the BGC per the Trevo IFU.

SR Combination	
Definition: Referred to as the “SR Combination” technique which involves using distal aspiration applied at the clot in conjunction with proximal flow control and a stent retriever.
 
Procedural technique: The BGC or LS is placed at the desired location. Using a guide wire, the aspiration catheter and microcatheter are navigated to the site of the occlusion – the aspiration catheter may be left proximal to the occlusion until retrieval begins. Position the microcatheter tip distal to the thrombus and remove the guidewire. The retriever is delivered through the microcatheter and is deployed per IFU. The retriever is allowed to expand and integrate into the clot and microcatheter is removed. [For BGC Only: Prior to retriever retraction, the BGC is inflated (to control antegrade flow in the ICA).] Aspiration is initiated and the aspiration catheter is navigated proximal to the clot. Aspiration is applied through the aspiration catheter and when there is no blood flow it has engaged the thrombus. The retriever and aspiration catheter are retracted together with care being taken not to bring the retriever all the way into the aspiration catheter.

Direct Aspiration	
Definition: Referred to as the “Direct Aspiration” technique which involves aspiration through the aspiration catheter.
 
Procedural technique: The BGC or LS is placed at the desired location. Using a guidewire, the aspiration catheter is navigated to the occlusion using the appropriate delivery catheter. Before aspiration, remove the delivery catheter and guidewire. Aspiration is applied through the aspiration catheter.

STRYKER CONFIDENTIAL - THIS DOCUMENT CONTAINS CONFIDENTIAL AND PROPRIETARY INFORMATION THAT IS THE PROPERTY OF STRYKER CORPORATION. NEITHER THIS DOCUMENT NOR THE INFORMATION HEREIN MAY BE REPRODUCED, USED, OR DISCLOSED TO ANY THIRD PARTY WITHOUT THE PRIOR WRITTEN CONSENT OF STRYKER CORPORATION.

Stryker Neurovascular

Document Title: ASSIST™ Registry Protocol

Document Number: CDM10001414

Rev: AB

Table 3. Examples of Technique Products

Technique Category	Technique	Products
SR Classic	1	SR (Trevo) + BGC (FlowGate ² or Merci)
SR Combination	2	SR (Trevo) + Asp Cath (AXS Catalyst DAC, Vecta) ± Pump + LS (AXS Infinity LS, AXS Infinity LS Plus)
	3	SR (Trevo) + Asp Cath (AXS Catalyst DAC) ± Pump + BGC (FlowGate ² or Merci)
Direct Aspiration	4	Asp Cath (AXS Catalyst DAC, Vecta) ± Pump + LS (AXS Infinity LS, AXS Infinity LS Plus)
	5	Asp Cath (AXS Catalyst DAC) ± Pump + BGC (FlowGate ² , Merci)

Note: Additional SNV products that are commercialized during the conduct of the Registry may also be included.

7.4 24 hours (-6/+24) Post Procedure

The following data will be collected at 24 hours (-6/+24) post procedure:

- NIHSS
- Imaging (CT, MR)
- Device and/or Procedure Related AEs
- All SAEs
- All Deaths

Any death or device and/or procedure related AEs and all SAEs should be reported to Stryker Neurovascular within 24 hours of becoming aware by eCRF completion. Available information regarding the primary cause of death and date/time of death will be recorded.

7.5 Discharge/Day 5-7 (whichever is earlier)

A subject may be discharged from the hospital at the Investigator's discretion. The following data will be collected between Day 5-7 (if subject remains in the hospital) or at discharge, whichever occurs first:

- mRS
- NIHSS
- Device and/or Procedure Related AEs
- All SAEs
- All Deaths

Any death or device and/or procedure related AEs and all SAEs should be reported to Stryker Neurovascular within 24 hours of becoming aware by eCRF completion. Available information regarding the primary cause of death and date/time of death will be recorded.

7.5.1 Post Discharge Follow Up

The designated staff at the clinical site will review the follow-up schedule with the subject to maximize compliance. The staff will instruct subjects to return for follow-up assessments according to the study Time

STRYKER CONFIDENTIAL - THIS DOCUMENT CONTAINS CONFIDENTIAL AND PROPRIETARY INFORMATION THAT IS THE PROPERTY OF STRYKER CORPORATION. NEITHER THIS DOCUMENT NOR THE INFORMATION HEREIN MAY BE REPRODUCED, USED, OR DISCLOSED TO ANY THIRD PARTY WITHOUT THE PRIOR WRITTEN CONSENT OF STRYKER CORPORATION.

Document Title: ASSIST™ Registry Protocol

Document Number: CDM10001414

Rev: AB

and Events Schedule in Table 4. Study staff should establish a date for the follow-up visits with the subject and if possible, schedule the visits at the time of hospital discharge.

The study will be considered complete after all subjects have completed the Day 90 (\pm 14) follow-up assessments or have discontinued the study early. Requirements of each follow-up evaluation are detailed below.

